***Part 3h: INCB001158 in combination with pembrolizumab in patients with malignant pleural mesothelioma.***

This cohort will enroll patients with advanced/metastatic malignant pleural mesothelioma that have received or were unable to receive standard front-line systemic therapy but have never received prior therapy with anti-PD-1/PD-L1, anti-CTLA4 or any other agent that specifically targets an immune checkpoint or co-stimulation pathway.

*A Simon's two-stage design will test the null hypothesis that the ORR  $\leq 0.13$  versus the alternative that ORR  $\geq 0.30$ . A total of 10 response-evaluable patients will be enrolled in Stage 1. If at least 2 patients respond (PR or better) out of 10 response-evaluable patients, then an additional 23 evaluable patients will be enrolled in Stage 2 (total of 33 response-evaluable patients). If Stages 1 and 2 are completed, a minimum of 7 patients must demonstrate a response (PR or better) to reject the null hypothesis*

Additional solid tumor cohorts may be added to Part 3 by protocol amendment based upon preclinical data, anti-tumor observations in Parts 1 and 2, and observations of clinical benefit. Up to 5 additional paired biopsies may be obtained in any cohort for which enrollment in Stage 2 is opened.

**6.0 SAMPLE SIZE**

Approximately 216 patients are planned for recruitment to the monotherapy and combination Dose Escalation cohorts. Approximately 148 patients are planned for recruitment in Stage 1 monotherapy and combination Expansion Cohorts. The number of patients may be increased in Stage 2 in each Expansion Cohort based upon observed anti-tumor activity. Assuming full enrollment of the Dose Escalation cohorts, including backfill patients (i.e., 12 patients per dose level for monotherapy and combination), and positive results in all Expansion Cohorts, up to 582 evaluable patients would be enrolled. Approximate recruitment estimates for Dose Escalation and each Expansion Cohort is shown in [Table 6.0-1](#).

**Table 6.0-1: Table of Sample Size Estimates**

	Approximate N	
Part 1a. Monotherapy Dose Escalation	up to 108	
Part 1b. Combination Dose Escalation	up to 108	
Part 1c. Combination in Patients with Moderately Impaired Renal Function	6 (evaluable patients will be counted towards Part 3 cohorts)	
Dose Escalation Total	up to 222	
	Stage 1	Stage 2
Part 2. Monotherapy Cohort Expansion		
2a. NSCLC	11	15
2b. CRC	11	15
2c. Assorted tumor types	30	30-50
2d. ██████████ ██████████	6	N/A
Monotherapy Expansion Cohorts (Total)	58	60-80
Part 3. Combination Cohort Expansion		
3a. NSCLC Prior Checkpoint	11	15
3b. Melanoma	11	15
3c. Urothelial carcinoma (prior PD-1/PD-L1)	11	15
3d. CRC (MSI-H) (prior PD-1/PD-L1)	11	15
3e. MSS CRC (PD-1/PD-L1 naïve)	11	15
3f. Gastric/GEJ (PD-1/PD-L1 naïve)	13	21
3g. SCCHN (PD-1/PD-L1 naïve )	12	13
3h. Mesothelioma (PD-1/PD-L1 naïve)	10	23
Combination Expansion Cohorts (Total)	90	132

**7.0 INCLUSION/EXCLUSION CRITERIA****7.1 Inclusion Criteria**

1. Patients must have a histological or cytological diagnosis of metastatic cancer or locally advanced cancer that is not amenable to local therapy. Additional criteria specific to different Parts/Cohorts of the study are provided below.
2. Ability to provide written informed consent in accordance with federal, local, and institutional guidelines
3. Age  $\geq$  18 years
4. Eastern Cooperative Oncology Group (ECOG) Performance Status of 0-1
5. Life Expectancy of at least 3 months
6. Adequate organ function as indicated by the laboratory values in [Table 7.1-1](#)

**Table 7.1-1: Laboratory Values for Inclusion**

Test	Value
Absolute neutrophil count (ANC)	$\geq$ 1,500/mcL
Platelets	$\geq$ 100,000/mcL
Hemoglobin	$\geq$ 9 g/dL
CrCl	All except Part 1c: $\geq$ 50 mL/min (calculated using the Cockcroft-Gault formula) Part 1c only: 30-49 mL/min (calculated using the Cockcroft-Gault formula)
Serum total bilirubin OR Direct bilirubin (for patients with Gilbert Syndrome and total bilirubin levels $>$ 1.5 ULN)	$\leq$ 1.5 X ULN OR $\leq$ ULN
AST (SGOT) and ALT (SGPT)	$\leq$ 2.5 X ULN
International Normalized Ratio (INR) or Prothrombin Time (PT)	$\leq$ 1.5 X ULN*

\* Does not apply to patients receiving therapeutic anticoagulation

7. Measurable Disease: At least one tumor lesion/lymph node that meets the RECIST v1.1 criteria for being “measurable.”
8. Willingness to avoid pregnancy or fathering children based on the criteria below:
  - a. Woman of nonchildbearing potential (ie, surgically sterile with a hysterectomy and/or bilateral oophorectomy OR  $\geq$  12 months of amenorrhea and at least  $>$  45 years of age.)

- b. Woman of childbearing potential who has a negative serum pregnancy test within three days before the first dose of study treatment and who agrees to take appropriate precautions to avoid pregnancy (with at least 99% certainty) from screening through safety follow-up (for patients receiving INCB001158 monotherapy) and until 120 days following the last dose of pembrolizumab. Permitted methods that are at least 99% effective in preventing pregnancy should be continued until 120 days after discontinuing should be communicated to the patient and their understanding confirmed.
  - c. Man who agrees to take appropriate precautions to avoid fathering children (with at least 99% certainty) from screening through safety follow-up (3 months following the last dose of study treatment). Permitted methods that are at least 99% effective in preventing pregnancy should be communicated to the patient and their understanding confirmed.
9. Resolution of all treatment-related toxicities, except alopecia, anemia, or endocrinopathies managed by hormone replacement, from any previous cancer therapy to  $\leq$  Grade 1 or to values within those required for eligibility on this study prior to the first dose of study treatment. Patients with long-lasting sequelae from prior anti-cancer therapy that have been demonstrated to be stable for  $> 3$  mo may be allowed if the Investigator and Medical Monitor determine that this will not compromise patient safety or interfere with the interpretation of the safety profile of INCB001158.

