#### **12.1.3.1 Dose Modification Guidelines**

Patients will be monitored continuously for AEs while on study. Treatment modifications (e.g., dose delay) will be based on specific laboratory and AE criteria.

INCB001158: Guidelines for AE management and dose modifications of INCB001158 due to AEs are provided in [Table 12.1-1](#). These guidelines are based on the clinical experience with

INCB001158 to date. These guidelines are intended primarily for toxicities that are not easily managed with routine supportive care. For example, alopecia does not require dose modification, nor does Grade 2 nausea/vomiting that is easily managed with anti-emetics.

INCB001158/pembrolizumab combination: Adverse events associated with pembrolizumab exposure may represent an immunologic etiology. These immune-related AEs (irAEs) may occur shortly after the first dose or several months after the last dose of pembrolizumab treatment and may affect more than one body system simultaneously. Therefore, early recognition and initiation of treatment is critical to reduce complications. Based on existing clinical study data, most irAEs are reversible and can be managed with interruptions of pembrolizumab and administration of corticosteroids and/or other supportive care. For suspected irAEs, ensure adequate evaluation to confirm etiology or exclude other causes. Additional procedures or tests such as bronchoscopy, endoscopy, and skin biopsy may be included as part of the evaluation. Based on the severity of irAEs, withhold or permanently discontinue pembrolizumab and administer corticosteroids. Dose modification and toxicity management guidelines for irAEs associated with pembrolizumab are provided in [Table 12.1-2](#). Management of irAES occurring on combination therapy should follow dose interruption/modification guidelines for INCB001158 and pembrolizumab outlined in [Tables 12.1-1](#) and [12.1-2](#), respectively.

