### **12.1.3.2 Resumption of Study Treatment**

For both INCB001158 and pembrolizumab, treatment may be delayed for up to 4 weeks from the last dose. Delays longer than 4 weeks are allowed only in cases where a prolonged steroid taper is required to manage drug-related AEs or, in some cases, if the delay was due to a

non-drug-related cause. Prior to re-initiating treatment in a patient with a dosing interruption lasting > 4 weeks, the Medical Monitor must be consulted. Treatment compliance will be monitored by drug accountability as well as the patient's medical record and eCRF.

Upon withholding study treatments for adverse events, the study treatments may be restarted when the AE has returned to  $\leq$  Grade 1. For patients that require a steroid taper, pembrolizumab should not be restarted until the steroid taper is complete. In cases in which a particular toxicity is clearly related to only one of the two study treatments, the study treatment that is not involved in causing the AE may be restarted prior to a return to  $\leq$  Grade 1. If INCB001158 is restarted after permanent discontinuation of pembrolizumab, INCB001158 should be permanently discontinued for a  $\geq$  Grade 3 recurrence of the AE that resulted in pembrolizumab discontinuation.

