Study drug-related creatinine increase  (patients with CrCl > 50 mL/min at baseline)	Grade 2 (> 1.5-3.0 X baseline OR > 1.5-3.0 X ULN)	Weekly testing of serum creatinine during interruption of study drug.	
 
Interrupt study drug.
 
1st event: Restart at same dose upon resolution to ≤ Grade 1.
 
2nd event: Restart at 25 mg BID upon resolution to ≤ Grade 1.
 

	Grade 3 (> 3.0 baseline; > 3.0-6.0 X ULN) or 4 (> 6.0 X ULN)	Weekly testing of serum creatinine during interruption of study drug.	
 
Interrupt study drug and do weekly serum creatinine testing and urinalysis until serum creatinine returns to ≤ Grade 1. Restart study drug at 25 mg BID.
 
If after 4 weeks the serum creatinine has not recovered to ≤ Grade 1, permanently discontinue study drug.
 
If after restarting study drug the toxicity reoccurs, permanently discontinue study drug.
 

Suspected immune-related adverse event (irAE) including: 
 
Colitis
 
Pneumonitis
 
Dermatitis
 
Hepatitis
 
Hypophysitis
 
Adrenal insufficiency
 
Type I diabetes mellitus
 
Nephritis
 
	Grade 1	
 
Symptomatic therapy, as appropriate
 
	No change
	Grade 2	
 
If > 5 days, 0.5 to 1 mg/kg/day prednisone. If worsening or no improvement, increase to 1 to 2 mg/kg/day prednisone equiv. and consider IV.
 
	
 
Interrupt study drug.
 
1st event: Restart at same dose upon resolution to ≤ Grade 1.
 
2nd event: Restart one dose level lower for second event of the same AE.
 

	Grade 3	
 
1 to 2 mg/kg/day prednisone equiv. Consider IV.
 
	
 
Interrupt study drug.
 
1st event: Consider restarting at next lower dose level upon resolution to ≤ Grade 1.
 
2nd event: Permanently discontinue.
 

	Grade 4	
 
1 to 2 mg/kg/day prednisone equiv. Consider IV.
 
	
 
Permanently discontinue.
 

**Table 12.1-1: INCB001158 Dose Modification Guidelines for Adverse Events in Patients Receiving INCB001158 (All Parts) (Continued)**

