Pneumonitis	Grade 2	Withhold	
 
Administer corticosteroids (initial dose of 1 - 2 mg/kg prednisone or equivalent) followed by taper
 
Add prophylactic antibiotics for opportunistic infections
 
	
 
Monitor participants for signs and symptoms of pneumonitis
 
Evaluate participants with suspected pneumonitis with radiographic imaging and initiate corticosteroid treatment
 

	Recurrent Grade 2, Grade 3 or 4	Permanently discontinue		
Diarrhea / Colitis	Grade 2 or 3	Withhold	
 
Administer corticosteroids (initial dose of 1 - 2 mg/kg prednisone or equivalent) followed by taper
 
	
 
Monitor participants for signs and symptoms of enterocolitis (ie, diarrhea, abdominal pain, blood or mucus in stool with or without fever) and of bowel perforation (ie, peritoneal signs and ileus)
 
Participants with <math>\geq</math>Grade 2 diarrhea suspecting colitis should consider GI consultation and performing endoscopy to rule out colitis
 
Participants with diarrhea/colitis should be advised to drink liberal quantities of clear fluids. If sufficient oral fluid intake is not feasible, fluid and electrolytes should be substituted via IV infusion
 

	Recurrent Grade 3 or Grade 4	Permanently discontinue		

**Table 12.1-2: Dose Modification and Toxicity Management Guidelines for Immune-Related Adverse Events Associated With Pembrolizumab (Parts 1b, 1c, and 3) (Continued)**

irAEs	Toxicity Grade (CTCAE V4.0)	Action With Pembrolizumab	Corticosteroid and/or Other Therapies	Monitoring and Follow-up
AST or ALT elevation or Increased Bilirubin	Grade 2 a	Withhold	
 
Administer corticosteroids (initial dose of 0.5 - 1 mg/kg prednisone or equivalent) followed by taper
 
	
 
Monitor with liver function tests (consider weekly or more frequently until liver enzyme value returned to baseline or is stable)
 

	Grade 3 b or 4 c	Permanently discontinue	
 
Administer corticosteroids (initial dose of 1 - 2 mg/kg prednisone or equivalent) followed by taper
 
	

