#### 13.1 Study Treatment Administration

##### INCB001158

Study drug (INCB001158) needs to be taken orally as capsule or tablet (25 mg or 100 mg per capsule or tablet) formulation. INCB001158 will be administered only to patients who have signed and dated an Informed Consent Form. Patients in Part 1a and 2: INCB001158 needs to be taken on Days 1 through 28 of each 28-day cycle and should be taken orally using the number of capsules or tablets directed in the Pharmacy Manual. [REDACTED]

[REDACTED] Patients in Part 1b and 3: INCB001158 needs to be taken on Days 1 through 21 of each 21-day cycle and should be taken orally using the number of capsules or tablets directed in the Pharmacy Manual. INCB001158 dosing will not be adjusted for body weight or surface area. Patients will continue to receive INCB001158 until disease progression (per irRECIST), intolerable toxicity, patient withdraws consent, or the Investigator determines that it is not in the patient's best interest to remain on study.

The study drug should be taken by the patient at approximately the same times each day on an empty stomach with a full glass of water. The first dose should be taken at least 2 hr before breakfast. The evening dose of INCB001158 will be taken approximately 12 hr later and at least 2 hr before or 1 hr after eating a meal. The effect of food is being evaluated in Part 1a during monotherapy dose escalation. If it is demonstrated that improved bioavailability can be achieved by taking INCB001158 with food, then patients thenceforth will take the drug with breakfast and dinner.

On PK days (see [Attachment 1](#)) patients should be instructed NOT to take their morning dose of INCB001158 at home. The morning dose must be administered at the clinical site after all pre-dose procedures have been performed. The time of dosing will be recorded in the clinic.

The evening doses will be self-administered by the patient after all post-dose activities have been complete.

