#### Pembrolizumab

Pembrolizumab will be administered on day 1 of each 3-week treatment cycle after all procedures and assessments have been completed as detailed on the schedule of assessment. Pembrolizumab will be administered as a dose of 200 mg using a 30-minute IV infusion. Sites should make every effort to target infusion timing to be as close to 30 minutes as possible. However, given the variability of infusion pumps from site to site, a window between -5 minutes and +10 minutes is permitted (i.e., infusion time is 30 minutes -5 min/+10 min). Patients will continue to receive pembrolizumab until disease progression (per irRECIST), intolerable toxicity, patient withdraws consent, or the Investigator determines that is not in the patient's best interest to remain on study. The maximum duration of pembrolizumab treatment on study will be up to 35 doses (approximately 2 years).

Pembrolizumab (Keytruda®) is supplied either as a 50 mg, lyophilized powder in single-use vials for reconstitution or as a 25 mg/mL sterile solution for infusion in 4 mL vials. The dose recently approved in the United States and several other countries for treatment of melanoma patients is 2 mg/kg Q3W. Please refer to the pembrolizumab Label/Investigator's Brochure for specific instructions on pembrolizumab administration.

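### Criterion 8b ties the only clear contraception end date for women on the combination to pembrolizumab, so read literally the rule can lapse while INCB001158 is still being taken

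*Protocol*

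**What the plan says.** Criterion 8b (Protocol Section 7.1) asks a woman of childbearing potential to avoid pregnancy "from screening through safety follow-up (for patients receiving INCB001158 monotherapy) and until 120 days following the last dose of pembrolizumab". The parenthesis attaches the safety follow-up end point to monotherapy. The other end point names pembrolizumab only. The next sentence says that permitted methods "should be continued until 120 days after discontinuing should be communicated to the patient"; it has lost part of its grammar and names no drug. Criterion 8c, for men, counts three months from the last dose of study treatment, and Section 13.0 defines study treatment as both drugs.

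The two drugs have different stopping rules. Section 13.1 limits pembrolizumab to 35 doses, about two years. For the other drug it says "Patients will continue to receive INCB001158 until disease progression (per irRECIST), intolerable toxicity, patient withdraws consent", or until the investigator judges otherwise, with no limit on duration. Section 12.1.3.1 adds that "Management of irAES occurring on combination therapy should follow dose interruption/modification guidelines for INCB001158 and pembrolizumab", each under its own table.

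**The concern.** Criterion 8b is the only place in the supplied text that sets a contraception period for women on the combination. INCB001158 is investigational. A site that applies the one clear end date could treat the requirement as over while a woman is still taking that drug.

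The other safeguards detect or respond to a pregnancy rather than prevent one. Attachment 1B schedules a pregnancy test at screening, at Cycle 2 and at End of Treatment. Section 11.3 adds on-treatment urine tests only when medically indicated or required by the country. Section 16.4 acts once a pregnancy is confirmed.

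**Working it through.** **Can INCB001158 outlast pembrolizumab?** The protocol foresees it in several places.

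- *Cap.* Pembrolizumab ends after dose 35; INCB001158 need not (Section 13.1).
- *Immune-related event.* In Table 12.1-2, pneumonitis of "Recurrent Grade 2, Grade 3 or 4" ends pembrolizumab permanently. In Table 12.1-1, the action for INCB001158 after a first Grade 3 immune-related event is "Consider restarting at next lower dose level upon resolution to" Grade 1 or less.
- *Severe enterocolitis.* Section 12.1.3.3 stops pembrolizumab for good, withholds INCB001158 and allows its restart to be considered.
- *General rule.* Section 12.1.3.2 has a provision that opens "If INCB001158 is restarted after permanent discontinuation of pembrolizumab".
- *After database lock.* Section 17.0 lets remaining patients stay on study treatment under usual care, with only SAEs and pregnancies still reported.

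**When does the stated requirement end?** Inputs: pembrolizumab on Day 1 of each 21-day cycle, at most 35 doses (Section 13.1), and 120 days (criterion 8b). Assumption: no dosing delays.

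- Day of dose k = 1 + 21(k − 1)
- End of requirement = 1 + 21(k − 1) + 120 = 100 + 21k

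| Last pembrolizumab dose | Day given | Requirement ends |
|---|---|---|
| k = 1 | 1 | 121 |
| k = 4 | 64 | 184 |
| k = 35 | 715 | 835 |

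Since 120 = 5 × 21 + 15, the end falls on Day 16 of cycle k + 5. Check for k = 35: Cycle 40 Day 1 is 1 + 39 × 21 = 820, and 835 − 820 + 1 = 16.

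**How long could the uncovered period be?** The documents do not say how long INCB001158 continues alone. If it is taken for m days after the last pembrolizumab dose, the on-drug days beyond the stated requirement are max(0, m − 120). With m assumed, these are illustrations, not estimates:

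| m (assumed) | Uncovered on-drug days |
|---|---|
| 120 or less | 0 |
| 150 | 30 |
| 183 | 63 |
| 365 | 245 |

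**Do the scheduled pregnancy tests close the period?** No. After one pembrolizumab dose the requirement ends in Cycle 6, and after 35 doses in Cycle 40. The Cycle 2 test comes before either, and the End of Treatment test comes after treatment has stopped.

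**Does a re-anchored rule close it?** Let P and L be the last days of pembrolizumab and INCB001158, and F the length of safety follow-up. Section 11.5.1 gives F as 30 to 37 days for all patients, with a further visit at 90 to 97 days in Parts 1b and 3. An end date of max(L + F, P + 120) is later than L for any F above zero, so no on-drug day is left out, whichever visit applies.

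**The case against.** The strongest reply is that ordinary readings already cover these women. Once pembrolizumab has ended, a woman taking only INCB001158 is, in plain words, on monotherapy. Safety follow-up counts from the final dose of study treatments, so she stays covered. Likewise, 120 days after discontinuing can be taken to mean all study treatment. The Amendment 2 summary, which describes superseded text, mentions 120 days beyond the last dose and is consistent with that intent.

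Both readings are possible; neither is secure. Section 12.1.3.3 sets monotherapy patients against combination patients and still uses the combination label after pembrolizumab has been permanently stopped. The second sentence of 8b names no drug. If it covers all study treatment, it disagrees with the monotherapy end point just before it, although that conflict would only lengthen contraception.

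Other parts of the reply stand:

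- Criterion 8 records willingness at entry, and patient instructions usually sit in the consent form. That form was not available and may state a fuller period, so nothing can be inferred from its absence.
- Section 12.1.3 lets a dose-escalation patient with a DLT continue INCB001158 only if pembrolizumab can continue.
- Section 12.2 takes patients with infusion delays over 35 days off study unless the Medical Monitor approves. If that applies to permanently stopped infusions, much prolonged INCB001158-alone use would already need individual review.

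A reader might infer that the protocol permits contraception to stop during INCB001158 treatment. It does not: no passage tells a site to allow this. A reader might also infer that women need 120 days after the last INCB001158 dose. The documents give no basis for that, since monotherapy women stop at safety follow-up after the same drug.

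**Conclusion.** The point holds as a drafting defect in a participant-protection rule. The only clear end date for women on the combination is anchored to the wrong drug, and the wording that might rescue it is ambiguous. A literal reading lets the requirement end between day 121 and day 835, depending on the number of pembrolizumab doses given on schedule.

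The exposed group is limited to women of childbearing potential in Parts 1b, 1c and 3 who take INCB001158 for more than 120 days after their last pembrolizumab dose. It is probably small, and its size cannot be derived from the documents. Endpoints, sample size and analysis are unaffected. The change is worth making because it is nearly free and removes reliance on interpretation.

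**What to change.** Replace the time limits in criterion 8b with: *from screening, throughout treatment with INCB001158 or pembrolizumab, and until the later of (i) the end of safety follow-up after the last dose of INCB001158 and (ii) for Parts 1b, 1c and 3, 120 days after the last dose of pembrolizumab.*

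Repair the second sentence so that it refers to the same period, for example: *Methods with at least 99% effectiveness are to be used for this whole period; the site explains them to the patient and confirms that she has understood.*

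Cost: wording in Section 7.1 and, if it repeats the rule, in the consent form. Contraception lasts longer only for women who keep taking INCB001158 for some time after pembrolizumab ends. In Parts 1b and 3, limb (i) becomes the later date once INCB001158 runs more than 120 − 97 = 23 to 120 − 90 = 30 days past the last pembrolizumab dose. A woman who stops both drugs in the same 21-day cycle has at most 20 such days, and 20 + 97 = 117 is below 120, so her end date does not move. No extra visits are needed.
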